### **12.3 Expectedness**

The assessment of whether or not an Adverse Reaction is an expected reaction from the administration of the IMP will be provided by the Chief Investigator (or Clinical Reviewer Delegate), it will not be provided by the Investigator responsible for the care of the participant.

This assessment will be based on the approved Reference Safety Information for the IMP indicated.

### **12.4 Reporting procedures**

Depending on the nature of the event, the reporting procedures below should be followed. Any questions concerning adverse event reporting should be directed to the study coordination centre in the first instance. A flowchart is given below to aid in the reporting procedures. The reporting procedure is depicted graphically in the flowchart Figure 2.

#### **12.4.1 Non serious AR/AEs**

Potential side effects will be recorded in the participant's dairy over the first 4 weeks of their participation. The parent/carer(s) will completed the diary and highlight the severity of any non-serious AR/AEs.

#### **12.4.2 Serious AR/AEs**

Fatal or life-threatening SAEs and SUSARs should be reported to the Trial Manager within 24 hours of the local site becoming aware of the event. The SAE form asks for the nature of event, date of onset, severity, corrective therapies given, outcomes and causality (i.e. unrelated, unlikely, possible, probably, definitely). The responsible investigator should sign the causality of the event. An SAE form should be completed and faxed to the study coordination centre for all SAEs within 24 hours. Additional information should be sent within 5 days if the

reaction has not resolved at the time of reporting. SAE reporting and processing procedures will be included in the training of all sites and research site staff.

**No assessment of expectedness will be provided by the Investigator responsible for the care of the participant.**

#### **12.4.3 SUSARs**

In the case of serious, unexpected and related adverse events, the staff at the site should:

Complete the SAE case report form and send it immediately (within 24 hours, preferably by fax), signed and dated to the study coordination centre together with relevant treatment forms and anonymised copies of all relevant investigations.

#### **OR**

[figure not shown]
Contact the CREAM Trial Manager by phone and then send the completed SAE form to the study coordination centre by fax within the following 24 hours as above.

The study coordination centre will notify the MHRA and main Research Ethics Committee (REC) of all SUSARs occurring during the study according to the following timelines, **where day zero is defined as the date the SAE form is initially received at SEWTU:**

- SUSARs which are fatal or life-threatening must be reported not later than 7 calendar days after the sponsor is first aware of the reaction. Any additional relevant information must be reported within a further 8 calendar days.
- SUSARs that are not fatal or life-threatening must be reported within 15 calendar days of the sponsor first becoming aware of the reaction.

Local investigators should report any SUSARs and/or SAEs as required by their Local REC and/or Research and Development Office.

Figure 2: Flowchart for Adverse Event Reporting Procedures

## **13 Trial procedures**

### **13.1 Training of staff**

All staff involved in the trial specific procedures (including recruitment/consent, collection of trial data, application of interventions and clinical assessments) will be trained in GCP.

#### **13.1.1 Training of research nurses**

The research nurses involved in the clinical aspects of this trial will be selected by the PIs of each region, who will ensure that they have the relevant skills, qualities and experience and up-to-date GCP training.

Prior to recruiting participants, the research nurses will attend a trial-specific workshop, which will include training in practical assessment of children with eczema, the IMP prescribing and dispensing procedure (how to receive, log and process patient's referred from general practices), assessing eligibility, informed consent procedures, taking swabs and training parents in taking swabs; and data collection procedures (including administering the validated outcome measures). An example of the planned training programme is provided in Appendix VII.

#### **13.1.2 Training of staff at sites**

Clinicians at sites will receive training to ensure they understand the CREAM protocol and how to refer patients using Trial Torrent or by contacting the research nurse directly. All staff at the sites with delegated responsibility for any aspect of the CREAM study will be provided suitable training to ensure they understand the referral procedure.

Practices using Trial Torrent will have remote support and local researcher assistance to ensure suitable data collection and referral of patients by sites.

#### **13.1.3 Training of staff at Site Pharmacies**

Staff at Site Pharmacies will work in accordance to their Standard Operating Protocols (SOPs) to receive, store and dispense the Trial Packs. All Site Pharmacies will be initiated formally during which training will be provided for relevant trial-specific SOPs to explain prescription handling, pharmacovigilance and Trial Pack handling.

### **13.2 Data collection/assessments**

The schedule for timing, frequency and method of collection of all trial data is summarised in Table 1. Assessments will be performed as close as possible to the required time point.

Where an assessment cannot be performed within a reasonable timeframe around the required time point, this will be documented in the research nurse log and/or participant's CRF, including the reason for missing the assessment (e.g. parent cancelled appointments).

### **13.3 Baseline assessments**

Once the patient is referred to the research nurse, the research nurse will contact the parent/carer(s) to arrange an appointment for the baseline visit at their home (or other suitable location). Prior to the baseline assessment, the research nurse will attend the Site Pharmacy and collect the Trial Pack(s) for that participant.

Once informed consent has been obtained the research nurse will:

1. Register the participant and their parent/carer(s) to the trial.
2. Conduct a standardised interview with the parent/carer(s).
3. Conduct a standardised examination of the child, including assessment of the EASI score.
4. Ask the parent/carer(s) to complete the POEM, IDQoL/CDQLI, DFI outcome measures, the resource use (as shown in Table 1) and the health utility (see Section 10.3) instrument.
5. Take swab samples from the child's infected eczema, nose and mouth.
6. Provide the parent/carer(s) with the study medication, and provide instructions on use of study medication.
7. Provide the parent/carer with standardised advice about caring for a child with eczema.
8. Give the parent/carer(s) a four-week symptom diary and provide them with instructions on diary completion.

The research nurse will arrange to re-visit the participant and their parent/carer(s) at 2 and 4 weeks following their initial visit. The research nurse will also advise parent/carer(s) that there will be telephone and postal follow-up at 3 months, and that the parent/carer(s) will be asked to take swab samples from the participant (infected eczema, nose and mouth) at 3 months and 12 months.

**Table 1: Table Summary of data collection**

Time Point	Baseline Evaluation	Follow Up Period				
		2 weeks	4 weeks	4 Week Diary	3 months	12 months
Data Method of Collection	Face-to-face	Face-to-face	Face-to-face	Completed daily by parents	Questionnaire/telephone + postal swabs	GP medical record search + postal swabs
Demographics, presenting features	X					
Swab eczematous skin	X	X			X	X
Swabs anterior nares and oropharynx	X	X			X	X
POEM	X	X	X		X	
EASI	X	X	X			
IDQoL/CDLQI	X	X	X		X	
DFI	X	X	X		X	
Health utility (see Section 10.3)	X	X	X		X	
Medication use				X		
Parental preference for treatment						
Daily symptoms				X		
Adverse effects		X		X		
Resource use	X		X	X	X	X
Consultations and antibiotic use for eczema				X		X

\*Weigh unused medication

## **13.4 Follow-up assessments**

The research nurse will re-visit participants and their parent/carer(s) at 2 and 4 weeks following the initial visit. The nurses will make every effort to visit at these exact time points, but if for any reason it is not possible to visit on the exact follow-up dates then they will be asked to visit as close as possible to the date in question within the thresholds: 2 week visit, -1/+3 days; and 4 week visit, -3/+3 days. There will be telephone and postal follow-up at 3 months and a medical-record search at 12 months. Swab samples (infected eczema, nose and mouth) will be collected at 2 weeks, 3 months and 12 months and returned in postage-paid packaging to the Specialist Antimicrobial Chemotherapy Unit (SACU), Cardiff.

### **13.4.1 Week 2: Research nurse visit**

The research nurse will record medication use and collect any unused study medication and provide ongoing support for the parent/carer(s); collect data for the outcome measures (EASI, POEM, IDQoL/CDLQI, DFI, and health utility (see Section 15.4); and collect the first 2 weeks data from the symptom diary. The RN will provide the parent/carer(s) with training in taking the swabs. Swabs will again be collected from the infected eczema, nose and mouth of the participating child and returned in postage-paid packaging (Section 13.5).

### **13.4.2 Week 4: Research nurse visit**

The research nurse will provide ongoing support for the parent/carer(s); collect information for the outcome measures (POEM, EASI, IDQoL/CDLQI, DFI, and health utility (see Section 10.3)); collect the final 2 weeks of the 4 symptom diary; and ask parent/carer(s) two short questions regarding any difficulties they may have had answering the health utility questions.

### **13.4.3 Month 3: Telephone and postal follow-up**

Three months following the recruitment of each participant, the parent/carer(s) will be contacted by letter, requesting that they take and return the 3-month swab samples. As a reminder to take and return the swabs at 3 months, parent/carer(s) will have swabs and postage-paid packaging posted with instructions on taking, handling and postal return of the swabs (Section 13.5).

Parent/carer(s) will also be send postal questionnaires to complete. This will involve completing information for outcome measures (POEM, IDQoL/CDLQI, DFI, and health utility (see Section 10.3)), and answering some questions about resource use.

If the questionnaire and/or packaging is not returned within 1 week, the research team will conduct telephone interviews. The interviewer will also encourage collection of the 3-month swab samples (Section 13.5).

#### **13.4.4 Month 12: Mouth and nose swabs**

Twelve months following the recruitment of each participant, the parent/carer(s) will be contacted by letter, requesting that they take and return the 12-month swab samples. Parent/carer(s) will have swabs and postage-paid packaging posted to them as a reminder to take and return the swabs at 12 months (Section 13.5). If the sample is not returned within 1 week, the research team will telephone the parent/carer(s) to remind them.

#### **13.4.5 Month 12: Medical Record search**

Data will be extracted from the primary care medical records for each participant for the 12-month period following recruitment. GP practices will be visited by a member of the research team or a clinical study officer or research nurse working for the local research network; or be asked to conduct a search of their practice records and send them to the study team at 12 months following recruitment of their last participant. The record search will be used to identify healthcare consultations (primary and secondary care), drugs prescribed, subsequent episodes of infected eczema, and use of antibiotics for the infected eczema.

### **13.5 Collection of swab samples**

Swabs will be collected at baseline, 2 weeks, 3 months, and 12 months. Swabs will be taken from suspected infected eczema to identify *S. aureus* or Group A Streptococcus infection, nasal swabs for *S. aureus* carriage, and oral swabs to identify any change in frequency of penicillin or macrolide resistance in Group A Streptococcus commensal flora. Research nurses will take the baseline and 2-week swabs and parent/carer(s) will be asked to take the swabs at 3 months and 12 months.

The research nurses will provide parent/carer(s) with training in taking swabs during the 2-week visit. Parent/carer(s) will be sent a postal reminder and packaging at 3 months and 12 months. Parent/carer(s) will be provided with swabs, a postage-paid packaging for returning the swabs, and written instructions on collecting them, prior to these two collection points.

The research nurse or delegated member of the research team will contact the parent/carer(s) who have not returned the swabs by telephone in order to remind them to do so. In addition, if the parent/carer is contacted by the research team

about the questionnaire or contacts the research team for any other reason, the researcher will again encourage collection of the specimens. Collection of nasal swabs is likely to be the most difficult for the carers. In addition to providing training, we will be using short swabs that cannot be inserted too far into the nose. Such an approach has been shown to be feasible in other studies , even when this involves deeper swabbing (from the turbinates) .

### **13.6 Microbiology processing**

The Specialist Antimicrobial Chemotherapy Unit (SACU) in Cardiff will receive the samples and log the date and time of receipt of the three different samples alongside the Patient ID and Date of Birth.

Nasal swabs will be cultured and any *S. aureus* will be confirmed and semi quantitative counts determined along with antimicrobial susceptibilities.

Infected eczema swabs will be cultured and *S. aureus* and Streptococci identification/grouping will be confirmed and semi quantitative counts determined along with antimicrobial susceptibilities.

Oropharyngeal swabs will be cultured and any streptococcus species found on non-selective and antimicrobial selective media will be confirmed and quantitative counts determined.

All isolates will be stored at -80°C storage. SACU will enter data into their own database which will be transferred securely to the Data Manager every month and merged with the CREAM database. To ensure all samples are returned at their required time points, SACU will inform the Trial Manager or Data Manager within 24 hours of receiving samples. The Data Manager will monitor the return of swabs and follow up with parent/carer(s) if any swabs are missing. Further details of the microbiology process, will be defined in a study-specific microbiology manual.

## **14 Statistical considerations**

### **14.1 Randomisation**

The study statistician will prepare randomisation tables for the randomisation of sites (General Practices) (for use of Trial Torrent) and participants. Further details of the randomisation process are provided in the randomisation protocol.

## **14.2 Primary Outcome Measure**

The primary outcome will be an assessment of subjective severity at two weeks as measured using the validated Patient-Oriented Eczema Measure (POEM). The POEM is based on symptoms over the previous week and therefore will be measuring symptom severity during the week following the end of experimental treatment, the period when a treatment effect is most likely. We have chosen a subjective measure for our primary outcome in recognition of the importance of measuring effects that are of importance to patients. POEM has been shown to be valid and reliable, easy to complete, sensitive to change, and is recommended for use in trials of AD.

## **14.3 Secondary Outcome Measures**

Subjective eczema severity will also be measured using the POEM at 4 weeks, and 3 months. Objective eczema severity will be measured using the Eczema Area and Severity Index (EASI). Quality of life will be assessed using the Infants Dermatology Quality of Life instrument (IDQoL) (for children aged 3 months to under 4 years old) and Children's Dermatology Life Quality Index (CDLQI) (for children aged 4 years to under 8 years), and impact on the family will be measured using the Dermatitis Family Impact (DFI) instrument. These are both well-validated, short, easy to use instruments, and we have expertise in our team in using them. A four-question condition-specific, preference-based measure of health for children will be used for the exploratory cost utility analysis.

A daily diary will be used to record symptom severity, medication use, carers' preference for treatment (recorded at 2 weeks), and healthcare resource use during the first 4 weeks. The diary will record the following symptoms each day: carer's assessment of overall severity, itch, sleep disturbance, oozing or weeping, bleeding, fever, and possible adverse effects (nausea, vomiting, diarrhoea, abdominal pain, joint pains, and new rash). We will pilot this diary with a sample of carers prior to use in the trial. We have had success in using daily symptom diaries in a number of studies, including four-week diaries, and diaries completed by parents/carer(s). One study successfully collected daily diary data from the majority of parents/carers for eight weeks. There is also evidence for the reliability and validity of diary data recorded by parents/carer(s).

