At the baseline visit, a trained research nurse will assess the extent and severity of eczema, quality of life, and impact of the eczema on the family, and health status, using established assessment tools. At the 2 week visit the research nurse will collect unused medication. At 2 and 4 weeks, the research nurse will visit to assess severity, quality of life, and impact on the family, as well as asking about side effects and costs (so that we can conduct an economic evaluation). The parent/carer(s) will be asked to complete a diary for the first 4 weeks to record symptom severity, use of medication, and healthcare consultations. Participants will also be followed-up by a postal or telephone questionnaire at 3 months (participants who do not return the postal questionnaire will be telephoned to see if they would prefer to complete a telephone-administered questionnaire), to assess eczema severity, quality of life, impact on the family, and costs. At 12 months we will conduct a search of participants' primary care medical records in order to identify healthcare consultations, drugs prescribed, subsequent episode of infected eczema and use of antibiotics for the infected eczema. We will take skin, mouth and nose swabs at the baseline and the 2 week visit, and ask the parent/carer(s) to take these swabs at 3 and 12 months, to assess impact of treatments on bacterial resistance. Asking parents to take swabs has been shown to be effective and acceptable to parent/carer(s) and children. Training on how to take these swabs will be provided to parents by the research nurses during the 2 and 4 week follow-up visits.

The main analysis will compare subjective eczema severity during the second study week (i.e. the week following completion of treatment), using established questionnaires completed by the child's parent/carer(s), in those in each of the two active treatment groups (oral and topical antibiotics) with the placebo group.

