### 5.2 Secondary objectives

- Assess the short-term (up to four weeks) effectiveness of oral and topical antibiotics on subjective and objective severity, quality of life, impact on family, and daily symptoms.
- Assess the effectiveness of oral and topical antibiotics on subjective and objective severity, and quality of life at 3 months.
- Compare oral and topical antibiotic treatments in terms of short and long-term effects, adverse effects, parent preference, and effect on prevalence of colonisation/infection with resistant organisms.
- Assess the short and long-term cost-effectiveness of treating suspected atopic eczema with oral or topical antibiotics, in terms of cost per unit reduction in subjective outcome severity.
- Undertake an exploratory cost utility analysis using a new condition-specific preference-based measure of health for children.
- Describe the prevalence of *Staphylococcus aureus* isolates, and patterns of resistance, in patients with suspected infected eczema, and describe the long-term prevalence of resistant isolates in those using oral antibiotics, topical antibiotics, and placebo.

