### **12.1.5 Suspected Unexpected Serious Adverse Reactions (SUSAR)**

These are **SARs** which are classified as 'unexpected', i.e. an adverse reaction, the nature and severity of which is not consistent with the information about the medicinal product outlined in the Investigator Brochure (IB) and SmPCs.

Example expected adverse reactions with trial treatments are listed below (and provided in detail in each medicine's SmPC):

- *Oral erythromycin*

Disorder	Examples
Blood and lymphatic system	Eosinophilia
Cardiac	QTc interval prolongation, torsades de pointes, palpitations, and cardiac rhythm disorders including ventricular tachyarrhythmias
Ear and labyrinth	Deafness, tinnitus (There have been isolated reports of reversible hearing loss occurring chiefly in patients with renal insufficiency or taking high doses.)
Gastrointestinal	Upper abdominal discomfort, nausea, vomiting, diarrhoea, pancreatitis, anorexia, infantile hypertrophic pyloric stenosis, Pseudomembranous colitis
General disorders and administration site conditions	Chest pain, fever, malaise
Hepatobiliary disorders	Cholestatic hepatitis, jaundice, hepatic dysfunction, hepatomegaly, hepatic failure, hepatocellular hepatitis
Immune system disorders	Allergic reactions ranging from urticaria and mild skin eruptions to anaphylaxis
Investigations	Increased liver enzyme values
Nervous system disorders	Isolated reports of transient central nervous system side effects including confusion, seizures and vertigo. (A cause and effect relationship has not been established.)
Psychiatric disorders	Hallucinations
Renal and urinary disorders	Interstitial nephritis
Skin and subcutaneous tissue disorders	Skin eruptions, pruritus, urticaria, exanthema, angioedema, Stevens-Johnson syndrome, toxic epidermal necrolysis, erythema multiforme
Vascular disorders	Hypotension

- *Oral flucloxacillin*

Disorder	Examples
Blood and lymphatic system	Neutropenia (including agranulocytosis), thrombocytopenia, haemolytic anaemia.
Immune system	Anaphylactic shock (exceptional with oral administration), angioneurotic oedema
Gastrointestinal	Minor gastrointestinal disturbances, Pseudomembranous colitis
Hepato-biliary	Hepatitis and cholestatic jaundice
Skin and subcutaneous tissue	Rash, urticaria and purpura Erythema multiforme, Stevens-Johnson syndrome and toxic epidermal necrolysis
Musculoskeletal and connective tissue	Arthralgia, myalgia
Renal and urinary	Interstitial nephritis

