General disorders and administration site conditions	Fever

- *Topical fusidic acid*

Disorder	Examples
Immune system	Hypersensitivity

Eye	Conjunctivitis
Skin and subcutaneous tissue	Pruritus, rash including erythematous, maculo-papular and pustular reactions, contact dermatitis, irritation at site of application (including pain, stinging, burning and erythema).

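### The daily diary prompts for the reactions expected from the oral drugs but, rash apart, not for the application-site reactions expected from fusidic acid, so the oral versus topical adverse-effect comparison may under-count local effects of the cream.

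*Protocol*

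**What the plan says.** Section 5.2 sets the comparison as a secondary objective: "Compare oral and topical antibiotic treatments in terms of short and long-term effects, adverse effects, parent preference". Section 4.2 gives the same motive, asking which route does less harm.

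Section 12.4.1 makes the parent diary the main route for non-serious events: "Potential side effects will be recorded in the participant's dairy over the first 4 weeks of their participation". Its next sentence has the parent mark the severity of any non-serious event, without restricting this to named items.

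Section 14.3 gives the daily content in two parts. The symptom items are "carer's assessment of overall severity, itch, sleep disturbance, oozing or weeping, bleeding, fever". The adverse-effect items are "possible adverse effects (nausea, vomiting, diarrhoea, abdominal pain, joint pains, and new rash".

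Section 12.1.5 lists the expected reactions. For erythromycin the gastrointestinal entry begins "Upper abdominal discomfort, nausea, vomiting, diarrhoea". For fusidic acid the skin entry includes "contact dermatitis, irritation at site of application (including pain, stinging, burning and erythema", alongside pruritus and several types of rash.

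There is also a nurse enquiry. Section 3.1 describes the 2 and 4 week visits as covering severity and quality of life, "as well as asking about side effects and costs". Table 1 marks adverse effects at the 2 week visit and in the diary, but not at 4 weeks. Sections 13.4.1 and 13.4.2, which describe those two visits, mention no adverse-effect question.

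**The concern.** A fair comparison of harms needs each treatment's characteristic harms to be looked for with similar effort. Here the typical effects of the oral drugs are prompted by name every day for four weeks. The typical effect of the cream, a local reaction where it is applied, has no prompt of its own. Parents tend to answer what they are asked, so a prompted effect in one arm would be set against a largely volunteered effect in the other.

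This is a matter of data collection. An analysis plan can decide how to tabulate the events, but it cannot recover events that were never recorded. If the report then found fewer adverse effects with the cream, a reader could not tell how much of the difference came from the drug and how much from the list.

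**Working it through.** **1. Diary items against expected reactions** (sections 14.3 and 12.1.5)

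| Expected reaction | Drug | Adverse-effect item in the diary |
|---|---|---|
| Nausea, vomiting, diarrhoea, abdominal discomfort | Erythromycin; minor gastrointestinal upset also for flucloxacillin | Yes, four items |
| Arthralgia | Flucloxacillin | Yes, joint pains |
| Rash or skin eruption | All three drugs | Yes, new rash |
| Site pain, stinging, burning, erythema | Fusidic acid | None specific |
| Contact dermatitis | Fusidic acid | None specific; new rash may catch some |
| Pruritus | Fusidic acid, erythromycin | Itch, but recorded as an eczema symptom |
| Conjunctivitis | Fusidic acid | None |

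Five of the six items match only the oral lists; the sixth, new rash, matches all three drugs.

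**2. What the other routes add**

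- Open reporting under section 12.4.1 covers any event, but the diary content described in section 14.3 gives no prompt for a local reaction.
- The 2 week visit has a window of -1/+3 days (section 13.4), so it falls on day 14 - 1 = 13 to day 14 + 3 = 17. Treatment lasts 7 days. If it starts on the baseline day, the question comes 13 - 7 = 6 to 17 - 7 = 10 days after the cream stops. The wording of the question is not given.

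**3. What the double dummy leaves at risk**

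Groups 1 and 3 apply a placebo cream on the same schedule (section 11.2). Reactions to the vehicle are missed or caught alike in every arm. What can distort the oral versus topical contrast is the excess of local reactions on fusidic acid over placebo cream, multiplied by the fraction that no route captures.

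**4. How much could that matter? An illustration under assumed rates**

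The protocol gives no adverse-effect rates. The only figure taken from it is 137 followed up per arm (section 14.4). As a check, 2 × (2.2414 + 1.2816)² × (7/3)² = 135.1, so 136 against the stated 137, which is close enough.

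Assumptions: the true any-event rate p is equal in the oral and topical arms, and all oral-arm events are recorded. A share s of topical-arm events are local only, off the list and in excess of placebo cream. A fraction c of those is caught by other routes. Then:

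- Recorded topical rate = p × [1 - s(1 - c)]
- Apparent advantage of the cream d = p × s × (1 - c)
- Chance of a two-sided 5% test favouring the cream ≈ Φ[(d - 1.96 × SE0)/SE1], with SE0 pooled and SE1 unpooled

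Example with p = 20%, s = 50%, c = 0: the recorded rates are 20% and 10%, so d = 10 points. SE0 = √(2 × 0.15 × 0.85/137) = 0.0431 and SE1 = √((0.16 + 0.09)/137) = 0.0427. The chance is Φ[(0.10 - 0.0846)/0.0427] = 64%.

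| s | c | Apparent advantage at p = 10%, 20%, 30% | Chance of a false result favouring the cream |
|---|---|---|---|
| 25% | 0 | 2.5, 5, 7.5 points | 11%, 19%, 29% |
| 25% | half | 1.25, 2.5, 3.75 points | 5%, 8%, 10% |
| 50% | 0 | 5, 10, 15 points | 35%, 64%, 85% |
| 50% | half | 2.5, 5, 7.5 points | 11%, 19%, 29% |
| any | all | 0 | 2.5% (nominal) |

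The result depends mainly on c, which the protocol does not secure.

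**The case against.** The strongest reply is that the six named items are not the whole system. Section 12.4.1 covers any non-serious event. Table 1 marks a face-to-face adverse-effect enquiry at 2 weeks, after the whole course of cream, and silence in section 13.4.1 does not cancel it. The diary itself is not reproduced, so it may already have a free-text line. New rash can pick up several of the fusidic acid reactions. The double dummy removes vehicle reactions from the comparison. Nor is the list complete for the oral drugs: jaundice, expected with both, has no item, and fever, also expected with both, sits among the symptoms just as itch does.

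Most of this stands, and it rules out some stronger readings. A reader might infer that the comparison favours the cream by construction, that local reactions are recorded nowhere systematically, or that the diary would capture none of them. The open wording, the 2 week enquiry and the rash item contradict each of these. A reader might also take an assumed 5% to 15% rate of stinging or burning, 7 to 21 of 137 children, as the number lost. That is not a measure of bias: the rate is assumed, it is not an excess over placebo cream, and it supposes that nothing else captures the events.

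What the reply does not remove is the inequality. Daily named prompts are a stronger method than volunteered reports or one question of unstated wording asked about a week after the cream stops.

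**Conclusion.** The concern holds as a risk of unequal ascertainment in one part of a secondary objective. The named items solicit the oral drugs' expected reactions. For the cream's characteristic local reaction, "irritation at site of application (including pain, stinging, burning and erythema", they offer no specific item. The likely direction is under-counting of any excess due to fusidic acid over placebo cream.

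The size cannot be stated from the protocol. Under the assumptions shown, the apparent advantage of the cream runs from zero, if the other routes capture everything, to 15 points in the most unfavourable case tabulated. With half the events captured it is 1.25 to 7.5 points. The conclusion rests on section 14.3 describing the diary accurately and on the nurse question containing no local-reaction prompt; if either is wrong, the problem shrinks or becomes one of wording. The disagreement between section 3.1 and Table 1 about week 4 is real but minor here, since the cream stops at day 7. The primary POEM comparison is unaffected.

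**What to change.** - **Diary (section 14.3):** add one daily item on stinging, burning, soreness or redness where the study cream was applied, and an 'other' line. If the diary in use already has these, correct section 14.3 to say so.
- **Nurse visit:** put the same local-reaction question into the 2 week visit in section 13.4.1, worded and asked identically in all three arms.
- **Consistency:** reconcile section 3.1 (side effects asked about at 2 and 4 weeks) with Table 1 (2 weeks only).
- **Reporting:** present local and systemic effects separately by arm, so that one combined count does not hide which kind was prompted.

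The cost is a diary reprint, a minor amendment and one or two more lines for parents each day. Children whose diaries are already complete will lack the daily item. The report must state this and should not pool the two diary versions for local reactions without comment.
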